6.2 Secondary Objectives

Table 2. Secondary Objectives

Objective		Estimand
Key Secondary		
To evaluate the change in weight of	a)	Population : The mITT population will be used for this analysis.
infants receiving Bi-26	b)	Endpoint : weight change (in grams) from baseline (Day 1) to the Day 56 visit in Bi-26 group.
	c)	Population level summary : Mean change from baseline in weight in the Bi-26 group compared to placebo with stratification blocking factors and feeding regimen covariate(s).
	d)	Intercurrent event(s): Including but not limited to treatment discontinuation.
Secondary		
To estimate the treatment response over time associated with Bi-26	a) b)	Population : The mITT population will be used for the analysis. Endpoint : WAZ change from baseline (Day 1) over time through the Day 90 visit (longitudinal assessment) by duration of dosing.
	c)	Population level summary : Mean change from baseline in WAZ over time in the Bi-26 group compared to placebo with stratification blocking factors and feeding regimen covariate(s).
	d)	Intercurrent event(s): Including but not limited to treatment discontinuation.
To assess the proportion of infants	a)	Population : The Safety population will be used for the analysis.
who achieve a specified change in WAZ from baseline to Day 56	re a specified change in b)	Endpoint : Proportion of infants with $a \ge 0.3$, 0.4, and 0.5 change in WAZ from baseline (Day 1) to Day 56 visit.
	c)	Population level summary : Frequency and percentages of infants with a ≥ 0.3 , 0.4, and 0.5 change in WAZ from baseline (Day 1) to Day 56 in the Bi-26 and placebo groups.
	d)	Intercurrent event(s): Including but not limited to treatment discontinuation.

Confidential Page 11 of 50

To assess the proportion of infants who achieve a specified WAZ at Day 56

- a) **Population**: The Safety population will be used for the analysis.
- b) **Endpoint:** Proportion of infants with a WAZ > -2 at Day 56 visit.
- c) **Population level summary:** Frequency and percentages of infants with a WAZ > -2 at Day 56 in the Bi-26 and the placebo groups.
- d) **Intercurrent event(s)**: Including but not limited to treatment discontinuation.

To assess the re-hospitalization rate

- a) **Population**: The Safety population will be used for the analysis.
- b) **Endpoint:** Number of re-hospitalizations for acute non-surgical illness through the Day 56 visit.
- Population level summary: Frequency and percentages of re-hospitalizations in the Bi-26 and the placebo groups.
- d) **Intercurrent event(s)**: Including but not limited to treatment discontinuation.

6.2.1 Secondary Objectives

The safety of Bi-26 supplementation will be evaluated through EoS in the Safety population which includes, but is not limited to, the frequency (and percentages) of AEs, and all SAEs through the Day 90 visit. Individual results and descriptive statistics will be provided by treatment group.

Individual results and descriptive statistics for presence of *B. infantis* in stool will be provided at each time point by treatment group.

6.2.2 Exploratory Objectives

The stool and blood biomarkers at specified timepoints will be analyzed using descriptive statistics. Details of any additional exploratory biomarker analyses, including potential engraftment analyses, will evolve from the initial test set to verification set. These will be included in separate operational and/or analysis plans. Results of these additional exploratory objectives will be reported separately from the main clinical study report.

Confidential Page 12 of 50

7 STUDY DESIGN CONSIDERATIONS

7.1 Study Design

This is a Phase 3, randomized, double-blind, placebo-controlled study to demonstrate increased weight gain with Bi-26 supplementation versus placebo in underweight infants (WAZ < -2) discharged from hospital following acute illness and to evaluate the safety of Bi-26 supplementation in this population.

Underweight infants (WAZ < -2), who are between 1 and 4 months of age (30 to 120 days) at enrollment and are currently hospitalized for acute non-surgical illness, will be enrolled to receive daily supplementation of Bi-26 or placebo for 28 days with a total study duration approximately 90 days.

Screening will take place during the infant's hospitalization, within a week of anticipated discharge. A participant discharged to a nutrition rehabilitation unit would still be considered a hospital discharge. Enrollment and randomization will take place on the day of hospital discharge (Day 1) and after the infant participant has completed the acute stabilization phase of treatment, including fluid rehydration and antibiotic course as needed. Screening may be conducted on the same day as enrollment/randomization (Day 1). Study assessments should not be duplicated if screening and Day 1 occur on the same day.

[figure not shown]
All participants will be given either Bi-26 supplementation, or product matched placebo (lacking the active ingredient), based on randomization. A single dose (Bi-26 or placebo control) will be resuspended, and administered to each participant, daily, for 28 days. Participants will be monitored for 30 minutes, and a repeat dose will be administered if a participant vomits within this observation period.

While a total of 7 doses are to be administered to the participant per week for a total of 4 weeks, 2 additional doses will be supplied each week to account for repeat dose administration in the event of vomiting, or unexpected events which may render a dose unusable (eg, spillage or otherwise compromised). Therefore, mothers will be dispensed 9 doses containing Bi-26 or placebo once a week, within 2 days before the doses are needed to ensure that doses are available when needed. Doses will either 1) be delivered to the mother by study staff, or 2) stored by staff, at the local health center to be picked up from health center.

Confidential Page 13 of 50

7.1.1 Study Schema

Figure 1. Study schema

Schedule of Activities is presented in Appendix 1.

7.1.2 Independent Data Monitoring Committee

While there is no formal interim analysis, an IDMC will review unblinded safety data during closed sessions and make recommendations to the sponsor. Separate TLFs will be developed for use in IDMC sessions according to the IDMC charter. A watermark will be used to distinguish between open and closed session TLFs.

7.1.3 Justification of Sample Size

[figure not shown]
The primary study hypothesis is that the difference in the mean change from baseline in WAZ is larger for participants randomized to at least 28 days of Bi-26 relative to placebo.

For the sample size calculation for the primary hypothesis, it is assumed that the between group difference in the WAZ change from baseline in 0.45 with a standard deviation of 1.3. Based on the above assumption(s) using a 2-sided alpha of 5% and a power of at least 90%, a total of 354 participants, 177 in each group are required.

Confidential Page 14 of 50

Assuming a 10% loss to follow-up and a 3% mortality rate, a sufficient number of participants will be screened to ensure approximately 396 randomly assigned participants are enrolled, 198 in each treatment group.

Figure 2. Sample size sensitivity

N/group, 1-sided $\alpha = 2.5\%$, Power=90%

7.2 Randomization and blinding

Randomization: On the day of hospital discharge (Visit 1, Day 1) participants will be randomized 1:1 to receive either Bi-26 or placebo. To minimize differences between Bi-26 and placebo groups within a given treatment arm, randomization will be stratified by:

- 1. Country (Bangladesh, Kenya, Pakistan, Tanzania)
- 2. Age at enrollment (Study Day 1):30 to 59 days of age, 60 to 120 days of age
- 3. Discharge destination (home, nutritional rehabilitation unit)
- 4. WAZ (< -3 versus > -3)

Dynamic randomization will be utilized to balance the treatment groups across the study population, site level, stratum level, and within stratification factors. Target randomization is approximately 2/3 of participants with WAZ between -2 and -3 and approximately 1/3 with WAZ \leq -3. The distribution of participants in WAZ strata will be monitored throughout the study in order to determine if a stratum needs to be temporarily/permanently closed for enrollment.

See Sections 11.5.1 and 11.6.6 for the calculations of age and WAZ to be used for stratification, respectively.

Confidential Page 15 of 50

7.2.1 Details of dynamic randomization

Treatment allocation will be done dynamically as participants are randomized. WAZ will be calculated in the Rave EDC system using sex, weight and age and the appropriate look-up table with a custom-built function. Rave RTSM will use the WAZ score calculated in the Rave EDC system for the stratification according to WAZ. Overall treatment balance of 1:1 between Bi-26 and Placebo will be achieved using dynamic randomization.

Dynamic randomization in Rave makes use of a covariate-adjusted dynamic allocation method [2, 4, 5, 6]. It is similar to other dynamic randomization methods by making use of an imbalance measure to assess how far off the allocations are from the targeted allocation between treatment arms, using weights to assign priority to stratification and study factors for treatment balance, and using the preceding allocations to assign the next treatment allocation.

In order to do the treatment allocation, the DACP algorithm in the Medidata Rave RTSM system will be used. The parameter CRP is a mandatory input which determines the probability of using either random allocation of treatments or using the minimization algorithm to determine the next treatment allocation. A random integer, say r_1 , is generated between 0 and 100. If

- $\frac{r_1}{100} \le CRP$ then the system picks the treatment allocation randomly between Bi-26 or Placebo with a probability of 50%
- $\frac{r_1}{100}$ > *CRP* then the system uses the minimization algorithm to assign treatment allocation based on imbalance scores.

A CRP of 15% is chosen to use the minimization algorithm in most of the treatment allocations. This will result in roughly 85% of treatment allocations to be assigned using the minimization algorithm. The final choice of the CRP was determined through simulations run in Medidata Rave RTSM, comparing different scenarios with different distributions of WAZ strata, different CRP values, as well as input from Medidata experts.

The weights used to assign the priority of balance to each factor is given by an integer value from 0 to 5 for each of the stratification variables (in this case WAZ, Age, Country, and Discharge destination) as well as for study (overall), stratum and site balance. The same weight is assigned to all levels of the stratification factors. The weights chosen for each of the relevant factors are presented in Table 3. The final choice of weights was also based on the simulations and expert input described above. High priority in balance is given to Study and WAZ as we aim for 1:1 ratio of treatments overall, and within WAZ strata.

The minimization algorithm determines the imbalance scores of assigning the next participant to be randomized to Bi-26 or Placebo. The treatment allocation least likely to cause imbalance based on these scores will be assigned.

The following formula is used to calculate the weighted imbalance score for treatment i:

$$Im_score_i = \sum_{j} w_j Im_{ij}$$

Confidential Page 16 of 50

where w_j is the weight associated with factor j and Im_{ij} is the relative imbalance due to assigning the next participant to be randomized to treatment i. The calculations for the different treatments are done separately, assuming the new participant is randomized to the respective treatment. Given that the target allocation between treatment groups is 1:1, that n participants have been randomized for factor j (in the level of the new participant), that m out of n participants have been assigned to treatment i, the relative imbalance for factor j and treatment i, Im_{ij} , is calculated as

$$Im_{ij} = 2 \times \left| 0.5 - \frac{m+1}{n+1} \right|$$

where

m: # participants already allocated to treatment i in factor j (relevant level)

n: # participants already randomized in factor j (relevant level)

Note that Im_{ij} is calculated assuming the n + 1th participant is randomized to treatment i.

Table 3. Weights Assigned to Factors Used in Dynamic Allocation

Factor	Weight
Study	3
Strata	1
Site	1
WAZ	3
Age	2
Age Country	1
Discharge destination	1

The final algorithm for treatment allocation of a participant is the following:

- 1. Determine the imbalance within factor, Im_{ij} , of assigning the next participant to treatment i, for each factor, given treatment allocations within each factor up to that point
- 2. Draw a random integer, say r_1 , between 0 and 100
- 3. If:
 - a. $\frac{r_1}{100} \le CRP$: assign next treatment allocation using a random draw (complete randomization).
 - b. $\frac{r_1}{100}$ > CRP: assign next treatment allocation using minimization.
- 4. Assign treatment allocation
 - a. If a random draw is used:
 - i. Draw random integer between 0 and 100, r_2 .
 - ii. If $\frac{r_2}{100} \le 0.5$ then allocate to Placebo.

Confidential Page 17 of 50

iii. If $\frac{r_2}{100} > 0.5$ then allocate to Bi-26.

b. If minimization is used:

- i. Use calculated imbalances scores, Im_score_{Pl} and Im_score_{bi26} for placebo and Bi-26 scores respectively.
- ii. If $Im_score_{pl} < Im_score_{bi26}$ assign the participant to Placebo.
- iii. If $Im_score_{Pl} > Im_score_{bi26}$ assign the participant to Bi-26.
- iv. If $Im_score_{Pl} = Im_score_{bi26}$ then a treatment is allocated randomly, as with complete randomization (see step 4(a) above).

7.3 Efficacy Measures

The following endpoints will be analyzed for primary efficacy analysis:

• Change in WAZ from baseline to Day 56 visit in the Bi-26 group.

For the secondary endpoints the following will be analyzed:

- Change in weight (in grams) from baseline to Day 56 visit in the Bi-26 group.
- Change in WAZ over time from baseline to Day 90 visit (longitudinal assessment) by duration of dosing.
- Proportion of infants with a $\geq 0.3, \geq 0.4$, and ≥ 0.5 change in WAZ from baseline (Day 1) to Day 56 visit.
- Proportion of infants with WAZ > 2 at Day 56 visit.
- Proportion of re-hospitalizations for acute non-surgical illness through Day 56 visit.
- Presence of *B. infantis* in engraftment stool samples on Days 1, 28, 56, and 90.

7.4 Safety Measures

The safety endpoints to be analyzed include:

- SAEs from Day 1 through the Day 90 visit (EoS)
- AEs from Day 1 through Day 90 visit (EoS)

7.5 Exploratory Measures

The following biomarker data will be collected to be used for exploratory samples:

- Fecal pH and Bristol or similar stool scale based on stool samples on Days 1, 28, and 56.
- Inflammatory biomarkers and host/or bacterial metabolic analysis on Days 1 and 28.

Confidential Page 18 of 50

8 STUDY POPULATIONS

8.1 Analysis Populations

Agreement and authorization of participants included/excluded from the PP population will be obtained prior to database lock and unblinding. A summary table containing the number of participants in each of the populations defined below along with any reasons for exclusions will be provided.

8.1.1 All Enrolled Participants

All participants randomly assigned to study intervention.

8.1.2 Intention to Treat Population

All participants randomly assigned to study intervention. A participant will be programmatically included in the ITT population if the participant has a randomization number and date. Participants will be analyzed according to the intervention they were randomized to.

8.1.3 Safety Population

All participants randomly assigned to study intervention, who received any dose, including a partial dose, of the study intervention. Participants will be analyzed according to the intervention they actually received.

8.1.4 Modified Intention to Treat Population

All participants randomly assigned to study intervention, who received at least one dose (including a partial dose) of the study intervention. Participants will be analyzed according to the intervention they were randomized to.

8.1.5 Per-Protocol (PP) Population

All participants randomly assigned to study intervention, who received the study intervention, have a Day 90 visit, and did not substantially deviate from the protocol procedures. Important protocol deviations will be evaluated individually by the sponsor to decide whether it has basis to exclude a participant from the PP population. Deviation from study intervention compliance (see Section 11.4) is defined as compliance of less than 80%. Participants will be analyzed according to the intervention they actually received (for details refer to Section 11.1).

8.2 Subgroups

To assess consistency of effects, subgroup analyses may be performed in selected subgroups such as:

- WAZ strata: < -3 and between -3 and -2 (boundaries excluded).
- Age: 30 to 59 days, 60 to 120 days.

Confidential Page 19 of 50

- Country: Bangladesh, Kenya, Pakistan, Tanzania.
- Discharge destination: Home, Nutritional Rehabilitation Unit.
- All participants who received 100% of doses during treatment.
- Method of delivery: C-section, vaginal birth.
- Bilateral pedal edema at baseline: Yes, No.
- Prior Infant Antibiotic use: Yes, No.
- Concomitant Infant Antibiotic/Probiotic use through Day 56 visit: Yes, No.
- Proportion of feedings through Day 56 from breastmilk: 100%, 75 to 99%, 50 to 74%, 25 to 49%, < 25%.

Other subgroups may be considered in the final analysis. Summary statistics for subgroups will be reported for subgroups with greater than 5 participants in each of the treatment arms. Further details on subgroup analysis are provided in the relevant efficacy and safety sections below.

Confidential Page 20 of 50

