11.3 Prior and Concomitant Medications and Procedures

A prior medication is defined as having started and ended prior to first dose of study intervention. A concomitant medication is defined as either having started prior to first dose of study intervention and ended on/after first dose of study intervention, is ongoing at Baseline or, having started on/after first dose of study intervention. Medications will be coded by site of action and therapeutic and clinical characteristics using WHO's ATC Classification.

The number and percentage of participants reporting prior and concomitant medications will be summarized separately by ATC Class and preferred name, by treatment group and overall.

The same table will be presented for concomitant medications for the mothers of the participants.

The following ATC class/terms for probiotics and antibiotics will be used to identify the participants for the subgroup analysis based on infant concomitant antibiotic/probiotic use (see Section 8.2):

- A07FA01 Lactic acid producing organisms (probiotics).
- A07FA02 Saccharomyces boulardii (probiotics).
- A07FA51 Lactic acid producing organisms, combinations (probiotics).
- J01 (antibiotics).
- J04 (antibiotics).

Prior/concomitant status (according to the definition provided at the start of this section) will be derived using the medication start and stop dates. For partial dates, see imputation rules in Appendix 2.

Reason for use, dates of administration including start and end dates, dosage information including dose and frequency of any medication or vaccine (including over-the-counter or prescription medicines, vitamins, and/or herbal supplements) that the participant was receiving at the time of screening or received during the study will be presented in participant listings for infants and mothers.

All procedures will be classified according to the latest version of MedDRA. The number and percentage of participants reporting concomitant procedures will be summarized separately by SOC and PT, by treatment. Concomitant procedures are defined as having been performed on or after the date of the first dose of study intervention. Procedures will be presented in a participant listing. The listing will include the start and stop dates of the procedures, whether it is related to an AE, reason for procedure, interpretation of procedure and findings.

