11.5.2.2 Subgroup analysis

Summary statistics may be presented by treatment and visit for subgroups as specified in Section 8.2 for WAZ. The mean difference in CFB with 90% confidence intervals between treatment and placebo will be presented at each visit.

A forest plot will be presented for selected subgroups showing the 90% CIs for mean CFB in WAZ at Day 56 visit by treatment group.

The mITT will be used for this analysis.

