11.5.3.2 Subgroup analysis

Summary statistics, including 90% confidence intervals for difference in CFB will be presented by treatment and visit for subgroups as specified in Section 8.2 for weight. The mITT population will be used for this analysis.

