11.6.1 Adverse Events

Safety assessments include SAEs and AEs from the time the ICF is signed through Day 90 (or at the date of last visit/study discontinuation).

An AE is considered treatment emergent if it started on or after the date of first dose of study intervention administration.

Confidential Page 37 of 50

An AE overview table containing the number and percentage (expressed in percent) of participants with AEs from Day 1 through Day 90 will be summarized by treatment group for the following:

- Any AE
- Any TEAE
- TEAEs related to study intervention
- TEAEs by maximum severity (Mild, Moderate and Severe)
- TEAEs leading to study intervention discontinuation
- TEAEs leading to study withdrawal
- Serious TEAEs
- Serious TEAEs with Outcome of Death

Additionally, the number and percentage of participants with AEs will be provided by SOC and PT and by treatment group for the following:

- Any TEAE
- TEAEs by maximum severity
- TEAEs related to study intervention
- Serious TEAEs
- Serious TEAEs related to study intervention

By-period summaries will be presented for TEAE and serious TEAEs by treatment group, where period is defined as in Section 10.1.

The overall AE summary table, AE table by SOC and PT and SAE table by SOC and PT will be presented by subgroups as specified in Section 8.2.

All AEs and SAEs will be classified according to the latest version of MedDRA.

SOC and PT will be sorted alphabetically by SOC and by decreasing frequency of preferred term in the all Bi-26 group (then alphabetically for ties). If a participant has more than one AE at a given level (eg, SOC and preferred term), the participant will only be counted once within that level. All summary tables will include the number of AEs. Missing severities and relationship will not be regarded as 'worst case'.

The following listings will be presented:

- All AEs through to Day 90
- SAEs through to Day 90

The AE listing by participant will display all reported AEs up to Day 90 and will include the verbatim term in addition to the SOC and preferred term. This listing will also include all relevant data associated with the event: eg, date of onset, date resolved, date of first dose, date of last dose, severity, whether AE is serious, outcome, relationship to study intervention, action taken with study intervention, and required therapy. When a date is presented, the study day

Confidential Page 38 of 50

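### Three of the ten SAP 8.2 subgroups are fixed after randomisation, yet between-arm differences and AE tables are planned on them with no label saying they are not randomised comparisons

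*SAP*

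**What the plan says.** SAP 8.2 names ten subgroups. Seven rest on information available at enrolment: WAZ, age, country, discharge destination, method of delivery, pedal edema at baseline and prior infant antibiotic use. The other three are:

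- a feeding grouping in five percentage bands, "Proportion of feedings through Day 56 from breastmilk: 100%, 75 to 99%, 50 to 74%, 25 to 49%, < 25";
- a dosing grouping, "All participants who received 100% of doses during treatment";
- a medication grouping, "Concomitant Infant Antibiotic/Probiotic use through Day 56 visit: Yes, No".

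SAP 8.2 says that analyses in selected subgroups *may* be performed, and that summaries are reported where each arm has more than 5 participants. The later sections are not uniform:

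| SAP section | Output | Wording |
|---|---|---|
| 11.5.2.2 | WAZ summary statistics | may |
| 11.5.2.2 | WAZ mean differences between arms, 90% CI, each visit | will |
| 11.5.2.2 | Forest plot, selected subgroups | will |
| 11.5.3.2 | Weight (key secondary) differences, 90% CI, each visit | will |
| 11.5.7.1 | Re-hospitalisation proportions | may |
| 11.6.1 | AE overview, AE by SOC/PT, SAE by SOC/PT | will |

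For weight: "Summary statistics, including 90% confidence intervals for difference in CFB will be presented by treatment and visit for subgroups as specified in Section 8.2". For safety: "The overall AE summary table, AE table by SOC and PT and SAE table by SOC and PT will be presented by subgroups", again with reference to Section 8.2. For the plot, which shows the arms separately: "A forest plot will be presented for selected subgroups showing the 90% CIs for mean CFB in WAZ at Day 56 visit".

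**The concern.** A subgroup comparison keeps the protection of randomisation only if membership is settled before treatment can influence it. Dosing completeness, antibiotic use through Day 56 and feeding pattern through Day 56 all develop while the infant is on study. If Bi-26 changes any of them, the Bi-26 and placebo infants inside a group no longer share the same underlying risk, and the difference mixes treatment effect with selection. Because SAP 8.2 gives consistency of effects as the purpose, a reader of the report could take such a difference for effect modification.

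The safety tables are the clearest case. Infants often receive antibiotics because of an adverse event, so splitting AE tables by antibiotic use partly splits them by the outcome. A real difference between arms can then shrink in both halves of the table.

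**Working it through.** **Is the antibiotic grouping really post-randomisation?** Protocol 5.1 requires any antibiotic course to be finished before enrolment, and Protocol 5.2 excludes ongoing infant antibiotic or probiotic use. SAP 11.3 counts as concomitant any medication "having started on/after first dose of study intervention". A Yes therefore arises almost only after Day 1.

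**Could treatment affect it?** The Protocol Introduction proposes that a *B. infantis* strain might interrupt recurrent infection and worsening malnutrition, and re-hospitalisation for acute illness is a secondary endpoint. On the plan's own hypothesis, antibiotic use could be a consequence of treatment.

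**Timing.** Differences are shown at each visit, so Day 28 results would be grouped by events up to Day 56. AEs run to Day 90, but the grouping stops at Day 56. Infants who die or leave early have less time to become a Yes.

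**Illustration 1: WAZ change with no true effect.** The SD of 1.3 is from Protocol 9.4. Everything else is assumed. An unmeasured frailty correlates 0.7 with the tendency to need antibiotics and -r with WAZ change. Antibiotic use is 40% on placebo (p0) and p1 on Bi-26. Let f(p) be the standard normal density at its upper-p point. The spurious Bi-26 minus placebo differences are:

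- users: -1.3 × r × 0.7 × [f(p1)/p1 - f(p0)/p0]
- non-users: -1.3 × r × 0.7 × [f(p0)/(1-p0) - f(p1)/(1-p1)]

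Example with r = 0.3 and p1 = 30%, where f(0.40) = 0.3863 and f(0.30) = 0.3477:

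- users: -0.273 × (1.159 - 0.966) = -0.053
- non-users: -0.273 × (0.644 - 0.497) = -0.040

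| r | p1 = 40% (users / non-users) | p1 = 35% | p1 = 30% | p1 = 20% |
|---|---|---|---|---|
| 0.2 | 0 / 0 | -0.017 / -0.013 | -0.035 / -0.027 | -0.079 / -0.053 |
| 0.3 | 0 / 0 | -0.025 / -0.020 | -0.053 / -0.040 | -0.119 / -0.080 |
| 0.5 | 0 / 0 | -0.042 / -0.034 | -0.088 / -0.067 | -0.197 / -0.134 |

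A simulation of 2,000,000 infants per scenario agrees to within 0.005, with an overall difference of about zero throughout. When Bi-26 lowers antibiotic use, both halves look worse for Bi-26 although nothing is wrong. When use is equal, there is no bias.

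**Illustration 2: AE tables.** Assumed: 80% of infants with an AE and 5% of the others receive antibiotics, and the true AE risk is 50% in one arm and 40% in the other.

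- Users: 0.50×0.80 / (0.50×0.80 + 0.50×0.05) = 94%, against 0.40×0.80 / (0.40×0.80 + 0.60×0.05) = 91%.
- Non-users: 0.50×0.20 / (0.50×0.20 + 0.50×0.95) = 17%, against 0.40×0.20 / (0.40×0.20 + 0.60×0.95) = 12%.

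A true gap of 10 points shows as about 3 and 5 points.

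**Precision at the smallest reportable size.** With 6 per arm, the 90% CI half-width for a WAZ difference is 1.645 × 1.3 × √(2/6) = 1.23 (normal approximation), against the planned effect of 0.45. This applies to any small subgroup, and the five breastmilk categories make small cells more likely.

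**The case against.** The strongest reply is that SAP 8.2 governs and only permits these analyses in selected groups, so the sponsor may drop the three. That is a fair reading of 8.2. A reader might infer from the later sections that all ten tables are mandatory, and the documents do not settle this. They do contain an unresolved conflict between *may* and *will*, and neither wording warns about the three groupings.

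Three further inferences go too far:

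- A reader might conclude from the forest plot that no subgroup treatment differences are planned. SAP 11.5.2.2 plans to tabulate them in the sentence before. The weakness is only that the figure shows arm means.
- A reader might take "WAZ strata: < -3 and between -3 and -2 (boundaries excluded" to mean that infants at exactly -3.00 fall in no subgroup. SAP 11.2 and 11.5.1 use ≤ -3, and 11.5.1 defines the other stratum as open at both ends. The missing equality may be a lost symbol, so this needs confirmation only.
- A reader might think a missing interaction test is a defect. The trial is sized for the main effect, and the SAP plans no subgroup p-values or claims. Such a test is optional.

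It is also true that these outputs are supportive, and that AE tables for the whole Safety population are planned as well. That limits the consequence. It does not make the split tables interpretable.

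**Conclusion.** The point holds for three of the ten subgroups. As written, SAP 11.5.2.2, 11.5.3.2 and 11.6.1 lead to between-arm differences and AE/SAE tables in groups formed after randomisation, without any label. The primary and key secondary mITT analyses and the seven baseline subgroups are not affected, and no sample size changes.

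The amount of bias cannot be derived from the documents, which give no antibiotic, dosing or feeding rates by arm. The figures above show direction and a plausible range for the antibiotic split only, under assumed inputs. A reader might infer that every such subgroup must understate the effect of Bi-26. That is not supported: the bias depends on how treatment shifts the grouping variable, is near zero if it does not, and was not worked out for dosing or breastmilk share.

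**What to change.** Amend the SAP before unblinding:

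1. In 8.2, reconcile *may* with the *will* of 11.5.2.2, 11.5.3.2 and 11.6.1.
2. Limit the between-arm differences (11.5.2.2, 11.5.3.2) and the AE/SAE subgroup tables (11.6.1) to the baseline subgroups. Primary feeding type since birth, already collected under SAP 11.2, can serve as the baseline feeding subgroup, although it covers a different period from breastmilk share on study.
3. If the three post-randomisation groupings are kept, show them only as separate descriptive summaries labelled as not randomised comparisons.
4. Make the forest plot show the Bi-26 minus placebo differences with CIs that 11.5.2.2 already plans to tabulate.
5. State the WAZ subgroup as the randomisation stratum in 11.5.1: WAZ ≤ -3 versus -3 < WAZ < -2.

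The cost is SAP wording and fewer tables, with no new data. What is lost is the between-arm look at fully dosed infants. The PP analysis replaces it only in part: it uses an 80% compliance cut-off, requires a Day 90 visit and is itself selected after randomisation. The compliance correlations in 11.5.2.3 also help only in part.
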